### **Funding**

There are no foreseen funding sources. However, some partnerships might be made to acquire some expenses that might exist (e.g., participants' insurance) and resources (i.e., equipment or human resources) needed to conduct the study.

## ABSTRACT

**Background.** Chemotherapy drugs carry many side effects that may hinder the functional performance of women with breast cancer (BC). Chemoresistance can lead to treatment failure. A relative dose intensity of chemotherapy <85% is associated with a worse diagnosis and lower treatment efficacy. Exercise may modulate treatment response through its effects on the tumor microenvironment and treatment tolerability. The need for a pleasant and sustainable exercise practice is important, considering the psychological and physiological stress that accompanies women with a BC diagnosis during treatment. Studies investigating the effects of exercise interventions on chemotherapy completion rates are needed.

**Purpose.** This study aims to investigate the effects of a self-selected intensity structured supervised home-based combined exercise intervention on the chemotherapy completion rates of women with BC. Secondly, we intend to analyze the impact of this intervention on functional performance, quality of life, body composition, and physical activity levels. A 3-month follow-up will investigate if physically active behavior is sustained post-intervention.

**Methods.** A 2-arm randomized controlled trial will be implemented in a real-world exercise setting to compare an online structured and supervised group aerobic and strength exercise intervention with an active control group during chemotherapy treatments. The study recruitment goal is 122 women with a BC diagnosis stage I-III who are scheduled to have neoadjuvant or adjuvant chemotherapy. Outcome measures will be obtained at baseline, mid-treatment ( $\approx$ 3 months), post-intervention ( $\approx$ 6 months), and 3-month follow-up. A mediation analysis will also be conducted.

**Key-words:** Breast cancer; Home-based exercise; Chemotherapy; Functional performance; Body composition; Physical activity; Quality of life

## Introduction

### Background and rationale

Breast cancer (BC) is the most diagnosed cancer type, with high levels of incidence, prevalence, and cancer-related deaths among women worldwide .

Chemotherapy is commonly used as an anticancer therapy, consisting of the intravenous administration of a combination of cytotoxic drugs to delay cancer growth or, in some cases, eradicate the tumor and prevent cancer cell multiplication, invasion, and metastasizing . However, since chemotherapy drugs are not selective to tumor cells or normal cells, many side effects hinder functional performance (i.e., a person's ability to perform daily activities involving physical effort with vigor and without excessive fatigue) of women with BC . Another problem that may arise during treatment is the development of tumor cells' resistance to chemotherapy, ultimately leading to treatment failure . A relative dose intensity (RDI) (i.e., the dose of drugs delivered to a person with cancer each week of treatment) <85% is associated with a worse disease prognosis and lower treatment efficacy .

Exercise appears to be a safe and effective cancer co-therapy that improves functional performance in women with BC during treatments and may potentially enhance treatment efficacy . Despite the very well-known benefits of exercise for women with BC, this population often fails to adhere to a more active lifestyle and comply with the recommended physical activity (PA) guidelines due to fatigue, conflicting scheduled commitments, sickness, forgetting appointments, pain, procrastination, and lack of self-discipline, enjoyment or interest .

Some evidence has shown that exercise may modulate treatment response through its effects on the tumor and may also improve the tolerability of chemotherapy, making it a potential tool to enhance chemotherapy completion rate (i.e., reception of the planned treatment doses) . So far, evidence shows that exercise does not disrupt chemotherapy delivery, but failed to demonstrate that exercise may increase chemotherapy completion rates . For instance, Mijwel et al. (2020) randomized 240 women to either a resistance and high-interval training group, aerobic and high-interval training group, or usual care groups and found no effects of exercise on chemotherapy completion rate. Sanft et al. (2023) conducted a home-based exercise and nutrition counseling intervention on 173 women with BC undergoing chemotherapy, reporting no intervention effects in RDI compared to the usual care group.

Home-based exercise interventions (i.e., programs performed inside or in the immediate surroundings of one's home ) are a convenient and flexible strategy with high adherence and proven to be effective and beneficial to improve functional

performance, raising activity levels, reducing symptoms, and improving overall quality of life in women with a BC diagnosis .

The need for a pleasant and sustainable exercise practice may be a relevant topic when considering the psychological and physiological burden and stress that often accompanies women after a BC diagnosis and during the treatment phase when dealing with therapy side effects . Even though some evidence suggests that allowing self-selection of exercise intensity may not be optimal to maximize health or fitness, increasing enjoyment and adherence to exercise practice and creating sustained lifestyle changes can be more beneficial . Although some exercise methods might be highly efficient in potentiating physiological outcomes in women with BC (e.g., high-intensity interval training), they may fail to meet this population's preferences and hinder the sustainability of active lifestyle behaviors after the studies' interventions .

Bolam et al. (2019) performed a 2-year follow-up on 206 women with a BC diagnosis who participated in either a concurrent high-intensity interval and progressive resistance training or a concurrent high-intensity interval training and continuous moderate-intensity aerobic exercise to analyze the PA levels of the participants post-intervention. Results showed that none of the participants in the intervention significantly changed their PA levels compared to the usual care group. Ramírez-Parada et al. (2019) conducted a questionnaire-based study on a sample of 112 women with BC to investigate the exercise preferences among this population, reporting that most participants preferred to perform the exercise in a group with other BC survivors at moderate intensity in a supervised setting. Studies have shown that participants can achieve adequate intensity and improve functional performance with exercise interventions where they self-select their training intensity in the general population . Evidence suggests that self-selected intensities seem higher when the participants are supervised by a qualified professional . Ratamess et al. (2008) investigated women's responses and the resistance training intensity selected, with and without professional supervision, in a healthy population. Findings in this study showed that women selected higher intensities, loads, and ratings of perceived exertion when supervised compared to unsupervised settings.

Also, evidence has shown that developing a program that is tailored and sensitive to the participants' needs and consider their preferences is essential to promoting continued engagement and long-term behavior changes . Gildea et al.  Schleicher et al.  stated that to maximize adherence to an exercise program and lifelong active lifestyles, the participants' preferences, facilitators, and perceived barriers must be considered.

Studies investigating the effects of exercise interventions on chemotherapy completion rates as a primary outcome are still needed to substantiate further findings. Also, to the authors' knowledge, no study has conducted and analyzed the effects of a structured and supervised home-based self-selected intensity exercise program in women with a BC diagnosis.

## **Objectives**

This study will investigate the effects of a structured, supervised, home-based combined exercise intervention with self-selected intensity on the chemotherapy completion rates of women with BC. We also intend to analyze the impact of this intervention on functional performance, body composition, PA levels, and quality of life. A 3-month follow-up will be performed to investigate short-term outcomes and active lifestyle sustainability post-intervention.

Hypothesis 1: Women in the intervention will have a better completion rate than those in the control group.

Hypothesis 2: Women in the intervention will present better functional performance, body composition, PA levels, and quality of life than the control group.

Hypothesis 3: In the post-intervention period, women in the intervention group will maintain a more physically active lifestyle than women in the control group.

## **Trial design**

This study will be a 2-arm pragmatic and superiority randomized controlled trial with an intervention and an active control group, with a 1:1 allocation ratio. It will comprise a structured, supervised, home-based combined exercise intervention that will start 1-2 weeks after chemotherapy treatments begin and continue until 3-4 weeks post-treatment. Additionally, a 3-month follow-up will be performed. This protocol followed the Spirit guidelines.

## **Methods**

### **Study setting**

The Home-Combo study will take place in the Algarve, and the sample will be recruited by medical referral from various public and private hospitals, and oncologic organizations across the region.

The intervention design will consider the PA/exercise preferences, perceived barriers, and facilitators of women with BC. This information will be collected before the intervention through a mixed-methods qualitative study that will include a survey and focus groups. The intervention will be conducted online to ensure the participants' safety during the chemotherapy treatment phase, as they may have compromised immunity. Also, this option was made to attenuate participants' burden caused by commuting requirements . Due to the specific timings between the first contact and study enrolment, participants will be enrolled continuously for one year. Recruitment will continue for each cohort until the number of participants per group is achieved. A scheme of the study timeline is presented in Table 1.

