### **Assignment of interventions**

#### **Allocation**

##### **Sequence generation**

After signing the informed consent form, participants will be given a number, randomly generated through Excel and emailed by a non-interventionist team member, which will be their participant number throughout the study. Participants will be instructed not to reveal their number to the research team or the other participants and to keep it with them until the end of the study. After all baseline assessments, participants will be randomly assigned to either the intervention or control arm through an online program (<https://www.graphpad.com/quickcalcs/randomize1/>). If recruitment takes longer than expected, adjustments in allocation may be made.

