### **Implementation**

After all questionnaires have been received, the random allocation will be performed. The non-interventionist team member will email all participants the numbers allocated in each group (intervention or control).

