### **Statistical methods**

All data will be analyzed using IBM SPSS (version 29.0). Factorial ANCOVAs with repeated measures will be used for the primary and secondary outcomes, adjusted for potential covariates (e.g., concomitant treatments, BC diagnosis, neo-adjuvant/adjuvant chemotherapy). Independent sample T-tests will be used to compare results between groups at each time point, considering chemotherapy completers versus non-completers . A Fisher's exact test will compare the proportion of participants who needed chemotherapy adjustments from those who did not . The intention-to-treat analysis will be conducted to ensure that all participants are included in the overall assessment, considering their compliance with the study protocol. The Last Observation

Carried Forward method will be used to input missing data values. A per-protocol analysis will also be conducted without participants who failed to complete at least 50% of the training sessions. Normality plots and Kolmogorov-Smirnov tests will be performed to test the normality of outcome variables. If normality is not satisfied, non-parametric tests will be applied (e.g., Krustal-Wallis). Mediators of change (i.e., mechanisms by which RDI) will be explored using structural equation modeling (AMOS 18.0) and multiple mediation analysis (PROCESS macro for SPSS). Putative candidates will include treatment (e.g., dose planned vs. given dose, planned cycles minimum/maximum, treatment interruption ratios, response to treatment, percentage of participants who needed dose adjustments, and the mean value of dose adjustment), and physiological (e.g., body composition, functional performance, handgrip strength, PA levels) variables. Mediation occurs when a causal effect of an independent variable occurs on a dependent variable, partly or entirely explained by a mediator. Indirect effects testing will be performed using Preacher and Hayes' procedures.

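### Women appear to be allocated in recruitment cohorts, but the named analyses leave cohort out; if arms are balanced within cohort, the between-group comparisons are slightly conservative

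*Protocol*

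**What the plan says.** All references are to the protocol.

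- **Trial design** sets the arms "with a 1:1 allocation ratio".
- **Study setting** states that "participants will be enrolled continuously for one year" and then that "Recruitment will continue for each cohort until the number of participants per group is achieved". Neither the number of cohorts nor their size is given.
- **Sequence generation** says: "After all baseline assessments, participants will be randomly assigned to either the intervention or control arm through an online program". It names no block or stratum and adds: "If recruitment takes longer than expected, adjustments in allocation may be made".
- **Implementation** says: "After all questionnaires have been received, the random allocation will be performed". The allocated numbers are then emailed to all participants together, which describes a batch procedure.
- **Statistical methods** says: "Factorial ANCOVAs with repeated measures will be used for the primary and secondary outcomes, adjusted for potential covariates", with examples that are all clinical. It also fixes independent-sample t-tests between groups at each time point and a Fisher's exact test for chemotherapy adjustments. Cohort is named in none of these.
- **Sample size** uses a repeated-measures factorial analysis with no cohort or block factor.

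**The concern.** Baseline and the start of exercise are tied to the first weeks of each woman's chemotherapy, and enrolment runs for a year. A single batch at the end of the year is therefore not feasible. The natural reading is that each cohort is allocated as a batch to a set number per arm, so that cohort acts as a randomisation block.

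When balance is forced within blocks, differences between blocks cancel out of the arm contrast. An analysis that leaves the blocks out still keeps those differences in its residual variance. The reported standard error is then larger than the true one, confidence intervals are too wide, and tests reject slightly less often than they should. Cohorts filled over a year could differ by season, which bears on walking and accelerometer outcomes, or in their mix of referring hospitals. What is at stake is some attainable precision, not bias.

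**Working it through.** **Inputs from the protocol.** 1:1 allocation; alpha 0.05; power 0.80; moderate effect size; 82 women before dropout and 98 after; four assessments, three of them for the primary outcome.

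**Assumptions, not in the protocol.** f = 0.25 for a moderate effect; correlation between repeated measures 0.5; number of cohorts; cohort share of variance (ICC); session-group size and ICC.

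**1. The plan's own figure.** For the between-groups test of a repeated-measures ANOVA with m measurements, lambda = f² × N × m / (1 + (m - 1) × rho). With N = 82 and m = 4, lambda = 0.0625 × 82 × 4 / 2.5 = 8.2, and power is 80.8%. So 82 is reproduced (with m = 3 the answer is 86). The 98 follows as 82 × 1.2 = 98.4. No step uses a gain from blocking.

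**2. Standard error without cohort.** With total variance 1 and balanced cohorts, the true variance of the contrast is proportional to 1 - ICC, while the model uses 1. Model SE / true SE = 1/sqrt(1 - ICC). At ICC 0.05 this is 1/sqrt(0.95) = 1.026.

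**3. Power at N = 82, m = 4, with 4 to 8 cohorts.** With a cohort term, lambda becomes 8.2/(1 - ICC), less one error degree of freedom per extra cohort. Without it, the same lambda is tested against the critical value divided by (1 - ICC).

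| Cohort ICC | SE overstated by | Type I error without cohort | Power without | Power with |
|---|---|---|---|---|
| 0 | 0% | 5.0% | 80.8% | 80.7% |
| 0.01 | 0.5% | 4.9% | 80.9% | 81.1% |
| 0.02 | 1.0% | 4.8% | 81.0% | 81.4-81.5% |
| 0.05 | 2.6% | 4.5% | 81.4% | 82.6-82.7% |
| 0.10 | 5.4% | 3.9% | 82.0% | 84.6% |
| 0.20 | 11.8% | 2.9% | 83.4% | 88.5% |

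**4. Simulation check of a two-group comparison at one time point.** 20,000 runs, 6 cohorts of 8 women per arm, true difference 0.57 SD (chosen so that 96 women give about 80% power).

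| Cohort share | Type I error without cohort | Power without | Power with | Difference |
|---|---|---|---|---|
| 0% | about 5% | 79.2% | 79.1% | -0.1 |
| 5% | 4.3% | 79.8% | 81.0% | 1.2 |
| 10% | 4.3% | 80.4% | 82.9% | 2.5 |
| 20% | 3.4% | 82.6% | 87.3% | 4.7 |

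The Monte Carlo standard error of a power near 80% is sqrt(0.8 × 0.2 / 20,000) = 0.3 points. The formula gives a somewhat lower type I error at 20% because it treats the cohort contribution to the residual as fixed, whereas with six cohorts it varies. Layouts of 4 cohorts of 12 and 10 cohorts of 5 per arm show the same pattern.

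**5. Group-by-time test.** A cohort effect that is the same at every assessment cancels from changes within a woman. Steps 2 to 4 therefore apply to the between-group comparisons, including the t-tests at each time point, and not to that interaction.

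**6. Session groups.** Exercise is delivered in online group sessions. If session group carries a variance share ICC_g with m women per group, model SE / true SE = sqrt(1/(1 - ICC_c - ICC_g + m × ICC_g)), taking clustering in both arms for simplicity. With m = 10, ICC_g = 0.03 and ICC_c = 0.05, this is sqrt(1/1.22) = 0.905, so the SE is too small. It is too large only when ICC_c exceeds (m - 1) × ICC_g, here 0.27. Simulated with clustering in the exercise arm only and 5% shares for both cohort and session group, type I error is about 6.4% without a cohort term and 7.3% with one.

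**The case against.** The strongest reply is that both conditions are supplied by inference. No section says that randomisation is blocked by cohort, cohort is never defined, and Sequence generation allows allocation to be adjusted. The data exclusions described under Blinding and Plans to promote retention could also disturb exact balance. This stands, and it is why the point is conditional. It does not remove the point: the number per group attached to each cohort, the batch allocation and the year of enrolment all lead to the same reading. If the ratio did shift between cohorts, leaving cohort out could also confound arm with calendar time.

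Three stronger readings are tempting, and the protocol does not support them.

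- *That the planned power is lost.* The 82 is reproduced without any blocking gain, and power without cohort stays at about 80% or above throughout. What is forgone is extra precision.
- *That no planned analysis will include cohort.* The ANCOVA adjustment is introduced by examples: "adjusted for potential covariates (e.g., concomitant treatments, BC diagnosis, neo-adjuvant/adjuvant chemotherapy". The list is open and may be completed in an analysis plan that is not at hand. The omission is firm only for the t-tests and Fisher's exact test.
- *That standard errors are simply too large.* Step 6 shows that group delivery can make them too small, and that a cohort term alone then makes the test slightly more liberal.

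It is also fair to say that nothing in the protocol supports a cohort share as high as 10 to 20%. Recruitment runs across several hospitals at once, and relative dose intensity is measured against each woman's own plan, so the share for the primary outcome may well be small.

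**Conclusion.** The point holds in a conditional and modest form. Allocation appears to be batched by recruitment cohort, and the analyses named in the protocol do not reflect this. If arms are balanced within cohort and cohorts differ in outcome, the between-group comparisons are slightly conservative, to the extent tabulated in steps 3 and 4. At a share of 0.05 or below the gain from adjusting is at most about 1 point of power, and at zero share adjusting costs about 0.1 point.

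These sizes rest on an assumed cohort share, cohort number and effect size, and on no session-group clustering. With such clustering the net direction can reverse. Nothing here threatens the validity of a positive result through the cohort omission itself. The reason to act is that aligning the analysis with the allocation is almost free.

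**What to change.** 1. In Sequence generation or Implementation, state that allocation is 1:1 within each recruitment cohort, and record the cohort in the dataset at allocation. Reconcile this with the sentence that permits adjustments in allocation.
2. In Statistical methods, name cohort as a factor in the ANCOVAs of the primary and secondary outcomes, replace the unadjusted between-group t-tests with cohort-adjusted comparisons, and stratify the comparison of proportions by cohort, for example with an exact stratified test.
3. Do not rely on the cohort term alone for valid standard errors. Account for session group in the exercise arm, either in the same model or in a sensitivity analysis.

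The cost is a few sentences, one extra recorded variable, and one degree of freedom per additional cohort (3 to 9 for 4 to 10 cohorts), with negligible loss if cohorts do not differ. The sample size need not change on account of the cohort term.

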### **Eligibility criteria**

Women aged  $\geq 18$  years with a BC stage I-III diagnosis, scheduled to receive neoadjuvant or adjuvant chemotherapy, and who have access to a computer will be considered eligible to participate in the study. Women already at the mid-stage of the chemotherapy treatments, with medical counterindication to perform the exercise intervention or physical assessments due to concomitant comorbidity, non-controlled health conditions or diseases, or psychological illness, currently enrolled in a structured exercise program, or women unable to complete the entire program (e.g., due to scheduled surgery or personal commitments) will be considered ineligible. Participants who get pregnant or have a worsening in their clinical condition during the intervention will be discounted from the program.

The exercise professionals who will perform the interventions and assessments must have an academic degree in Exercise Sciences and a specialization in exercise with cancer populations or receive education sessions with an exercise professional specialized in exercise for BC populations to acquire knowledge and skills to conduct exercise sessions online. Also, professionals who conduct the interventions will have to perform at least three simulated sessions among each other, supervised by a qualified peer, to guarantee consistency in the intervention application.

